Specific aim #1: Define functional nausea (FN) as an entity subdivided by measures of arousal, anxiety and gastric motor function.

Hypothesis: Adolescents with chronic nausea form subgroups based on clinical, physiologic and psychological parameters: 1) FN: characterized by high anxiety and emotional arousal, autonomic imbalance/low vagal tone and absence of major foregut dysmotility, 2) gastroparesis, and 3) poor gastric compliance. We will separate FN from other groups by clinical questionnaires, autonomic tests (heart rate variability) and gastric motility tests (gastric emptying, accommodation tests).

Specific aim #2: Demonstrate that resting state functional brain connectivity is different in female adolescents with FN compared to gender and age-matched healthy controls.

Hypothesis: Adolescents with FN will have altered rsFC between brain regions associated with emotional arousal neurocircuits (amygdala) and the top-down regulation of these by the prefrontal cortex. There will be decreased resting state functional connectivity between the ventromedial prefrontal cortex (vmPFC) and amygdala in adolescents with FN compared to healthy controls.

Specific aim #3: Demonstrate that four weeks of auricular neurostimulation improves nausea while strengthening the vagal tone and the abnormal resting state brain connectivity in female adolescents with FN compared to baseline and to more resemble that of healthy controls.

Hypothesis: 3a) Compared to baseline (pre-stimulation), there will be reduction in nausea and concurrent symptoms in the active compared to sham neurostimulation group after 4 weeks of therapy. 3b) Active neurostimulation therapy will increase vagal tone compared to baseline and also increase the rsFC between the vmPFC and amygdala in female adolescents with FN.

C. BACKGROUND, SIGNIFICANCE, AND RATIONALE

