Research-dedicated GE MR750 3.0 Tesla whole-body scanners with 32-channel phase-array head coil will be employed and the scanner is located in the Froedtert Hospital (FH)/Medical College of Wisconsin (MCW). Our scanning protocol will focus on integrating the most recent advances in multimodal imaging technologies, including T1 SPGR, T2 FLAIR, R-fMRI, and ASL-CBF images. The justifications of utilizing these imaging protocols are: 1) to noninvasively characterize the structural, functional, and metabolic changes in subjects; 2) these imaging protocols will provide robust quality control, repeatable and reliable imaging datasets for imaging post-processing and statistical analyses; 3) most of these imaging protocols and pulse sequences have been tested and released as products by major scanner vendors (GE, Siemens, and Philips), therefore, they can be immediately translatable to the clinic setting.

Specifically, the integrated multimodal imaging protocols and justification are summarized below:

1) SPGR high-resolution images. Acquire T1 weighted spoiled gradient recalled echo (SPGR) images for high spatial resolution of anatomical images. The SPGR images can be employed for tissue segmentation and volumetric analysis using FreeSurfer, and image registration for functional neural network studies.

2) FLAIR images. Acquire T2 weighted fluid attenuated inversion recovery (FLAIR) images for general pathological detection such as for macroscopic white matter lesion quantification, and micro hemorrhage. In addition, the T1/T2 ratio can provide myelination information.

3) R-fMRI images. Acquire resting state functional magnetic resonance imaging (R-fMRI) datasets to study intrinsic blood oxygenation level dependent (iBOLD) signal. These iBOLD signals will be employed to study changes in neural networks of the disease and control brains. It is hypothesized that a) alterations in functional cortical networks are apparent; b) Network wide analysis can identify and classify functional disease status together with their comorbidity. We will utilize “seed”-based, module-based, and whole brain network-based analyses to characterize the changes in nausea/pain brains. For the image acquisition, we will employ our newly developed pulse sequence, named Spatially compensated Intra-shot Turbo keyhole (SCITH), based on multi-echo denoise approach for robust reliability and repeatability for functional connectivity analyses.

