fMRI-guided connectivity analysis: We have developed a novel *fMRI-guided connectivity analysis* in previous investigations by [name] to determine the distribution of an arousal network by using a seed region in a specific brain area of interest. In this protocol, we will examine resting state functional connectivity with amygdala as the seed region of interest and its coupling with prefrontal cortex areas as well as insula and hypothalamus as key nodes of the emotional arousal neurocircuit and internal awareness.

Statistical Analysis

Data Management

The data gathered will be entered into REDCap data system with each ID having a unique identifier for each participant. REDCap is a secure, web-based application for building and managing online databases. All data will be de-identified and samples will only have a unique identifier that will link the unique identifier with the patient's name.

The REDCap clinical database will be maintained by the Department of Quantitative Health Sciences, at the Children's Research Institute under the direction of [name].

Missing Data Handling

Missing Data: Every effort will be made to avoid missing data. Using logistic regression, the pattern of missing data will be explored. Assuming the data are missing at random (MAR) multiple imputations for items will be used. Data analysis overview: Summary statistics, such as mean, median, standard deviation, range and correlation will be used as a first step to examine data. To satisfy parametric assumptions, we may perform transformations with justifications if possible and otherwise use non-parametric tests. We will use CART and biological and physiological information to identify interactions when formulating regression models. Statistical software employed for data analysis will be: Cytel StatXact, SAS version 9.4, Salford System CART for trees, SPSS Version 24. The power calculation was made using PASS 13.'

Power

Aim 1. We will summarize characteristics by the groupings.

Aim 2. See fMRI analysis section below

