Strategies for imaging data analysis and data fusion with clinical observation. The goal for analyzing results from integrated multimodal imaging protocols is provide structural, functional, and metabolic information for the insight into the mechanisms of pain/drug abuse brains in order to advance long-term prevention, diagnosis, prediction and treatment planning. Our strategy for analyzing these large complexes imaging datasets will involve four steps: **First step**, preprocess imaging datasets for individual subjects and then convert voxelwise imaging parameters into standard imaging matrices in MNI templates. **Second step**, conduct group-level statistical analysis based on each of imaging modalities, e.g. functional (R-fMRI) or ASL-CBF images. There are three levels of neural network analyses: 1) Seed-based network analysis; 2) ROI-based large scale network analysis; and 3) whole brain Graph theory analysis (e.g., Small-world graphical analysis). From the second step, we will obtain imaging parameters as independent variables for each subject such as brain atrophy, CBF and functional connectivity index (FCI) at seed, regions, and whole brain networks levels. **Third step**, construct a database containing demographic information and a battery of neuropsychological and behavioral testing scores. **Fourth step**, conduct Data fusion processes from step 2 and step 3 with **Multivariate analysis** and **Multivariate Linear Regression for establishing the neural biomarker for diagnosing and measuring treatment responses/efficacy**.

Multivariate analysis will be employed in determining the sensitivity and specificity in discriminating normal, pain, or drug abuse subjects as described in specific Aims. The imaging parameters ***P*** from step 2 (e.g. Functional connectivity index (FCI) and metabolic information (CBF) will be statistically combined to give a composite imaging Index, which will be employed in disease diagnoses. We propose to use a multivariate classification

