We will assemble these measurements for each of the n subjects into the $n \times m$ matrix \mathbf{Y} . The design matrix \mathbf{X} is an $n \times p$ matrix, $\mathbf{X}_j(t) = [X_{j1}(t) \ X_{j2}(t) \ \dots \ X_{jp}(t)]$. In this case, the regression coefficients, which relate the independent to the dependent variables, are represented by the $p \times m$ matrix $\boldsymbol{\beta}$. Then, the multivariate linear regression model is given by: $\mathbf{Y} = \mathbf{X}\boldsymbol{\beta} + \boldsymbol{\varepsilon}$, where $\boldsymbol{\varepsilon}$ is the error matrix. The error terms corresponding to the m cognitive observations for the j th subject may be correlated. Likelihood ratio tests will be performed to assess the statistical significance of various components of the regression coefficient matrix $\boldsymbol{\beta}$, in order to determine which subsets of the independent variables can be used to predict variations in cognitive ability across subjects.

MCW Research Team and imaging facility: MCW is a national leader with a well-established model for basic and clinical translational research. Our MCW research group was the first to discover and develop R-fcMRI methodology in 1995 and has been at the forefront in developing R-fcMRI applications for nearly two decades. Our group has previously used R-fcMRI to describe changes in neural networks in a variety of diseases and conditions, including cocaine/heroin abuse, mTBI, pain, Alzheimer's disease, depression, and anesthesia, etc. Also, MCI imaging research center, has a team of imaging physicists and imaging processing scientists and the-state-of-the- art GE MR750 3T scanner to conduct the proposed studies.

Outcome measure and Impact: The proposed study will provide biomarkers for the functional pathophysiology of functional GI disorders, as well as other comorbidities that can lead to improved diagnostic and treatment options for these debilitating conditions and ultimately improve the long-term health and welfare of functional GI disorders.

G. RISK CATEGORY:

Nausea and IBS patients - 45 CFR 46.405: Research involving greater than minimal risk but presenting the prospect of direct benefit to the individual child subjects

Healthy controls in fMRI sub-study - 45 CFR 46.404: Research not involving greater than minimal risk to the children

H. RISKS AND THE PRECAUTIONS WHICH WILL BE TAKEN TO MINIMIZE RISK EXPOSURE

Gastric function tests:

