Written informed consent for participation will be obtained from the parents and children for their child's participation. Written assent will be obtained from youth 12 and 13 years of age using the CHW assent form. Patients ages 14 and above will sign the assent line on the consent form per CHW policy. Consent will be obtained by a study investigator or member of the research team at the patients' appointment in the GI Clinic. Volunteers' consent will allow for accessing information collected for program evaluation/clinical purposes. Participating children and parents will have the option of having the consent/assent document read aloud to them to facilitate understanding. Copies of signed consent/assent documents will be given to participants. When consent is given for a minor child to participate in a research study by one or both parents, and the child reaches the age of majority (18 years) the child will be re-consented as an adult to continue participation in the study. If age of majority is reached while the participant is active and continues to receive study interventions per the study protocol, he/she will be re-consented using the most current approved IRB informed consent document and HIPAA form. If age of majority is reached after all study interventions have been completed and the participant remains in the study for purposes of data collection for outcomes only a separate "Age of Majority" informed consent will be obtained.

O. PROCEDURES TO BE EMPLOYED IN ANALYZING DATA AND THE ANTICIPATED SIGNIFICANCE OF THE PROPOSED STUDY

Analyses will be conducted with SPSS and SAS software programs. Probability levels of $< .05$ will be used as cut offs for statistical significance.

The key significance of this study is the identification of a successful, non-invasive therapy for chronic nausea and to study the underlying brain connectivity that may be altered by this therapy. With this study, we hope to lay the foundation for the application of auricular neurostimulation for pediatric functional GI disorders by demonstrating effects on brain network. This is an innovative and novel treatment, which will enhance our knowledge on the brain-gut neural connectivity underlying functional disorders and ultimately improve patient care.

P. FINANCIAL RELATIONSHIPS

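### Aim 2 can be read as met by any of several connectivity analyses, with none designated as confirmatory; if any may count, the chance of a false positive is about 2 to 4.5 times 5%

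*Combined protocol and SAP*

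**What the plan says.** All references are to the combined protocol and SAP.

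- **Section B, Specific aim #2.** The aim is: "Demonstrate that resting state functional brain connectivity is different in female adolescents with FN compared to gender and age-matched healthy controls". It names no region and no direction. The hypothesis beneath it first speaks broadly of altered connectivity between amygdala circuits and the prefrontal cortex, then becomes specific: "There will be decreased resting state functional connectivity between the ventromedial prefrontal cortex (vmPFC) and amygdala in adolescents with FN compared to healthy controls". Section C repeats the specific hypothesis in bold.
- **Section F, Statistical Analysis, Power.** For Aim 2 the reader is only referred to the fMRI analysis section.
- **Section F, fMRI analyses, second step.** "There are three levels of neural network analyses: 1) Seed-based network analysis; 2) ROI-based large scale network analysis", with whole-brain graph theory as the third. Neither vmPFC nor amygdala is mentioned in this section, and it gives no primary contrast, sidedness, alpha or power for Aim 2.
- **Section F, Multimodal Imaging protocols.** Seed-based analysis is listed again, alongside "module-based, and whole brain network-based analyses to characterize the changes in nausea/pain brains".
- **Section F, Resting State Functional Connectivity MRI and fMRI-guided connectivity analysis.** The amygdala is the seed. The first passage refers to prefrontal regions in the plural. The second examines "its coupling with prefrontal cortex areas as well as insula and hypothalamus as key nodes of the emotional arousal neurocircuit".
- **Section F, Data Acquisition and Analysis.** Statistical maps are corrected with AlphaSim cluster thresholding. The only group-level test named is a voxelwise one-sample t-test.
- **Section O.** Probability levels below .05 "will be used as cut offs for statistical significance".

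The other multiplicity statements do not reach Aim 2. The Bonferroni sentence concerns Aim 3 symptom scores, and the statements that no adjustment will be made concern efficacy variables.

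**The concern.** The hypothesis points to one connection, but nothing says that this connection decides Aim 2, and the section meant to cover Aim 2 leaves it out. A significant amygdala-insula result or graph metric would satisfy the literal wording of the aim even if amygdala-vmPFC connectivity showed nothing.

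Cluster thresholding limits false positives among voxels inside one map. It does not cover the choice among network levels, or among targets if these are tested separately. The comparison is 15 FN subjects with 15 controls, with no stated power. At stake is whether a positive Aim 2 report supports the mechanism the trial was built to test, and whether a reader could tell how many analyses were tried. The fMRI section also ends with the statement "The proposed study will provide biomarkers for the functional pathophysiology of functional GI disorders", and no imaging analysis is labelled exploratory.

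**Working it through.** The plan states no power, effect size or overall error rate for Aim 2, so there is no figure to reproduce. The check asks what the chance of at least one false positive would be if any connectivity analysis could count.

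**Inputs from the document**
- Cutoff: 0.05 (section O).
- Network levels: 3, namely seed, ROI and graph (fMRI analyses).
- Seed targets: prefrontal areas, insula and hypothalamus (fMRI-guided connectivity analysis).
- Group sizes: 15 FN and 15 healthy controls (section E).

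**Assumptions not in the document**
- Number of tests k. With one test per network level, k = 3. With the three seed targets tested separately, plus one ROI and one graph test, k = 5.
- Two-sided tests, one valid p-value per analysis, and a common correlation ρ between test statistics. The analyses use the same subjects and the same resting-state data, so positive correlation is likely; ρ is varied from 0 to 0.8.

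**Independent tests (ρ = 0)**

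Chance of at least one false positive = 1 − 0.95^k.
- k = 3: 1 − 0.95³ = 1 − 0.8574 = 14.3%
- k = 5: 1 − 0.95⁵ = 1 − 0.7738 = 22.6%

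**Equally correlated tests**

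With c = 1.96, the chance is

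1 − ∫ φ(x) [Φ((c − √ρ·x)/√(1−ρ)) − Φ((−c − √ρ·x)/√(1−ρ))]^k dx,

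evaluated by numerical integration.

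| k | ρ = 0 | ρ = 0.5 | ρ = 0.7 | ρ = 0.8 |
|---|---|---|---|---|
| 3 | 14.3% | 12.5% | 10.9% | 9.8% |
| 5 | 22.6% | 18.3% | 14.8% | 12.7% |

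Relative to 5%, the extremes are 9.8/5 = 1.96 and 14.3/5 = 2.9 for k = 3, and 12.7/5 = 2.5 and 22.6/5 = 4.5 for k = 5.

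**Check with t-tests at the planned size**

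A simulation of two-sample t-tests with 15 per group (100,000 replicates) gave 14.4%, 12.5% and 11.1% for k = 3 at ρ = 0, 0.5 and 0.7, and 22.6%, 18.5% and 15.2% for k = 5. The normal approximation is adequate here.

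**After the fix**

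With one designated contrast at 0.05, the error rate for the Aim 2 claim is 5%. Bonferroni over a listed family would also control it. For independent tests, 0.05/3 = 0.0167 each gives 1 − (1 − 0.0167)³ = 4.9%, and 0.05/5 = 0.01 each gives 1 − 0.99⁵ = 4.9%.

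**The case against.** The strongest reply is that Aim 2 already has a specific, directional hypothesis, stated in section B and repeated in section C, and that the amygdala is fixed as the seed. No sentence says that any connectivity difference meets the aim. If the stated hypothesis decides, there is no inflation across analyses. This is a fair reading and it limits the point: the inflation is conditional. It does not remove the point, because no sentence says that the contrast decides either, and the section to which Aim 2 is referred does not mention it.

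A second reply is that prefrontal areas, insula and hypothalamus may be locations in one amygdala seed map, already covered by AlphaSim. The document does not say whether they are tested separately. If they are one map, the three-test row applies. On the other side, ROI and graph analyses often yield several metrics each, and the section does not say how many, so one test per level may be too few.

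A reader might infer more than the document supports:

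- **Cerebral blood flow, atrophy and IBS contrasts as further routes to Aim 2.** Blood flow and atrophy do not measure connectivity, and Aim 2 compares FN with healthy controls only. None belongs in this arithmetic.
- **A fixed inflation of three to five times.** The multiple depends on assumed test counts and correlations. With three network levels it stays below three.
- **An explicit plan to test every imaging analysis at .05.** The cutoff is a general, study-wide sentence. The fMRI section gives no between-group threshold for ROI or graph measures.
- **The biomarker sentence as a success criterion.** It stands under outcome and impact and is not a decision rule.

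This is also an optional mechanistic sub-study. The trial's primary outcome, the Nausea Severity Scale, is unaffected.

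**Conclusion.** The point holds in a conditional form. The plan states one contrast as the Aim 2 hypothesis but does not make it the deciding test, lists several other connectivity analyses, and states no control across them. If any of these may count as meeting Aim 2, the chance of at least one false positive is about 10% to 14% for three network levels and about 13% to 23% for five connectivity tests, roughly 2 to 4.5 times 5%. This rests on assumed test counts, correlations from 0.8 to 0, two-sided testing and one valid p-value per analysis. If only amygdala-vmPFC connectivity decides, the rate is 5%. The document should say which reading applies before the imaging data are analysed.

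**What to change.** Add to the fMRI analyses section:

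> The single confirmatory imaging test for Aim 2 is baseline amygdala-vmPFC connectivity in FN versus healthy controls, two-sided alpha 0.05. All other targets, ROI-level and graph metrics, CBF, atrophy and contrasts involving IBS are exploratory. They are reported with the number of tests run and a false-discovery-rate adjustment within each level, and cannot by themselves support Aim 2 or a biomarker claim.

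The between-group test should be named in the same place, since only a one-sample voxelwise test is described now.

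The cost is wording only: no extra subjects, scans or visits, and every planned analysis can still be run. The downside is that findings outside the amygdala-vmPFC contrast become exploratory.

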Participants who are interested in learning more about the fMRI sub-study will indicate so on the main study consent form. A member of the research team will explain the sub-study to the participant and guardian(s). If the participant is willing to participate, the sub-consent and assent forms will be completed. [name] will complete a psychological history for all participants who agree to participate in the fMRI sub-study. Female participants in the experimental group (Nausea group; n=15 and IBS group; n=15) who are found to be eligible to participate in the sub-study will be scheduled to complete the fMRI scans at Visit 3 (baseline scan) prior to EAD placement and Post #1 (post-scan; day 5 after the last neurostimulator placement within one hour of removing the device). The post-scan will be compared to baseline and baseline scans from 15 age-and gender-matched healthy controls who will undergo one fMRI scan (no therapy). All ethnic categories will be included.

Healthy control participants will be recruited via word of mouth. Researchers will mention the study to peers who will be instructed to contact the research team to learn more about the study. A member of the research team will introduce the study either in person or over the phone and will explain the inclusion and exclusion criteria. If the participant is eligible, consent/assent documents will be completed. Participants will then be scheduled to visit the pTRU where they will meet with a study physician who will perform a brief medical examination to confirm participant eligibility. Eligible participants will be escorted to the MRI unit by a member of the research team where they will be introduced to the mock scanner. Participants will have the option of lying in the mock scanner prior to their fMRI scan. A medical professional who is a member of the research team will be present during the scan. Healthy controls will only have 1 fMRI visit which will be completed at their convenience.

fMRI Sub-study inclusion (FN and IBS Groups):

- meet general study inclusion criteria

fMRI Sub-study inclusion (Healthy Control Groups):

- Female children, aged 12 years to 18 years, who provide written assent and whose parents provide written permission for participation
- English-speaking

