technique, such as Fisher's Linear Discriminant Function. Assume that we have a training sample of n normal subjects, and m diseased subjects (nausea or pain). For each subject, we measure P parameters. Then, we can assemble this data into the matrices: $\mathbf{X}_1 = [x_{11}, x_{12}, \dots, x_{1,n}]$ and $\mathbf{X}_2 = [x_{21}, x_{22}, \dots, x_{2,m}]$, where x_{ij} = vector of P measurements for subject j from group i ($i=1,2$ (normal and diseased, respectively)). Let μ_1, μ_2 = sample mean vectors, and $\mathbf{S}_1, \mathbf{S}_2$ = sample covariance matrices, for the normal and diseased groups. The sample covariance matrices can be combined into a single, pooled estimate: $\mathbf{S}_{\text{pooled}} = [(n-1)\mathbf{S}_1 + (m-1) \mathbf{S}_2] / (n+m-2)$.

From these quantities, Fisher's Sample Linear Discriminant Function is given by:

$y(\mathbf{x}_0) = (\mu_1 - \mu_2) \mathbf{S}^{-1}_{\text{pooled}} \mathbf{x}_0$, where \mathbf{x}_0 represents a vector of observations for a new subject. Define q as the midpoint between the transformed sample means:

$$q = \frac{1}{2} [y(\mu_1) + y(\mu_2)] = \frac{1}{2} (\mu_1 - \mu_2) \mathbf{S}^{-1}_{\text{pooled}} (\mu_1 + \mu_2)$$

Then, using Fisher's Linear Discriminant Function, we classify \mathbf{x}_0 as belonging to the normal group if $y(\mathbf{x}_0) > q$, and classify \mathbf{x}_0 as belonging to the diseased group if $y(\mathbf{x}_0) < q$.

Based on these values of $y(\mathbf{x}_0)$, ROC curves can be constructed. Note: In order for the matrix inverse $\mathbf{S}^{-1}_{\text{pooled}}$ to exist, it is necessary that $n + m - 2 > P$.

Multivariate Linear Regression will be employed in determining the neural correlates of clinical parameters. The imaging parameters \mathbf{P} from step 2 will be the independent variables and clinical parameters \mathbf{M} from Step 3 will be the dependent variables. Therefore, in order to deal with multiple dependent and multiple independent parameters, across multiple subjects, we propose to use multivariate multiple regression models. Suppose that cognitive ability is measured as a vector of m components. That is, for each subject j in the study, we measure the vector \mathbf{m} of cognitive attributes at time t :

$$\mathbf{Y}_j(t) = [Y_{j1}(t) \ Y_{j2}(t) \ \dots \ Y_{jm}(t)].$$

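### The imaging classifier has no subjects beyond those used to fit it and no stated validation, so a high AUC can be expected without any signal unless the parameter list is very short and fixed in advance

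*Combined protocol and SAP*

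**What the plan says.** The fMRI analyses text in Section F sets the purpose: "Multivariate analysis will be employed in determining the sensitivity and specificity in discriminating normal, pain, or drug abuse subjects as described in specific Aims". A composite index, meant for diagnosis, is to be built from the scan measures. The candidates are atrophy, cerebral blood flow and connectivity indices at seed, region and whole-brain level.

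For the method it proposes a technique such as Fisher's discriminant: "Assume that we have a training sample of n normal subjects, and m diseased subjects (nausea or pain"). The group means and pooled covariance of that sample give the weights. The symbol x0 "represents a vector of observations for a new subject", and from the values y(x0) "ROC curves can be constructed". A closing note says that the pooled covariance can be inverted only if n + m − 2 exceeds P. P itself is given nowhere.

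The scanned subjects are described in Section D, Optional fMRI Sub-study: "Female participants in the experimental group (Nausea group; n=15 and IBS group; n=15"), and "15 age-and gender-matched healthy controls who will undergo one fMRI scan (no therapy"). Section E repeats these numbers. Patients are scanned again after therapy; controls are not.

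**The concern.** A discriminant chooses its weights to separate the subjects it is fitted to. If the same subjects are then scored, the ROC curve partly measures how well the weights have followed the noise. The effect grows with the number of parameters relative to the number of subjects.

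The plan's formula calls for new subjects, but none are provided. Post-therapy scans come from the same patients and so are not an independent test set. The separate normative protocol supplies gastric and HRV values, not scans. The other imaging protocol mentioned in Section F receives task data from these controls and supplies nothing for validation. The cluster-threshold correction under Data Acquisition and Analysis applies to voxelwise maps, not to the classifier.

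At stake is whether a reported sensitivity, specificity or AUC for the composite index can be told apart from overfitting. The fMRI analyses text intends that index for diagnosis and for measuring treatment response.

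**Working it through.** The plan states no AUC, accuracy or sample size for the classifier, so there is no result to reproduce. Its one numerical condition can be checked, and its formulas can be run on data with no signal.

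**Inputs**
- Controls: n = 15 (Sections D and E).
- Diseased group: the classifier text gives only the letter m and allows nausea or pain. One diagnosis gives m = 15; FN and IBS pooled give m = 30. Both are assumptions, and both are shown.
- P: not stated, so a range is used.
- Formulas from the fMRI analyses text: S_pooled = [(n−1)S1 + (m−1)S2]/(n+m−2); y(x) = (μ1 − μ2) S_pooled⁻¹ x; cut-off q = ½[y(μ1) + y(μ2)]; classify as normal if y > q.

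**Step 1: the invertibility note.** For 15 v 15, 15 + 15 − 2 = 28 > P, so P ≤ 27. For 15 v 30, 15 + 30 − 2 = 43 > P, so P ≤ 42. Simulated pooled matrices from 15 + 15 subjects had full rank at P = 27 and 28, and rank 28 (singular) at P = 29. The note is sound, but it guards only against a singular matrix.

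**Step 2: apparent performance with no signal.** Each setting used 3,000 simulated data sets, with independent standard normal parameters distributed identically in both groups, so the true AUC is 0.50. Fisher's discriminant is unchanged by linear transformation, so correlation between parameters would not alter the results. The table gives the AUC on the fitting subjects.

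| P | 15 v 15: mean AUC | 15 v 15: share with AUC ≥ 0.80 | 15 v 30: mean AUC | 15 v 30: share with AUC ≥ 0.80 |
|---|---|---|---|---|
| 1 | 0.582 | 0.3% | 0.572 | 0.1% |
| 2 | 0.632 | 1.7% | 0.613 | 0.3% |
| 3 | 0.668 | 5.4% | 0.644 | 1.2% |
| 5 | 0.725 | 17.5% | 0.694 | 4.6% |
| 8 | 0.798 | 50.1% | 0.750 | 22.0% |
| 10 | 0.837 | 71.5% | 0.784 | 40.3% |
| 15 | 0.921 | 97.7% | 0.855 | 84.0% |
| 20 | 0.974 | 100% | 0.908 | 97.8% |
| 27 | 1.000 | 100% | 0.966 | 100% |

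At P = 10 with 15 v 15, apparent sensitivity and specificity are both 0.76.

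**Step 3: the same rules on subjects outside the fit.** Scoring 200 + 200 independent new subjects gave a mean AUC of 0.499 to 0.501 at every P. Leave-one-out accuracy for 15 v 15 (300 runs per setting) averaged 0.487 to 0.505 for P = 1 to 25.

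**Step 4: selection on the same data.** If parameters are first picked by group difference (15 v 15, 2,000 runs), the mean apparent AUC under no signal is 0.72 for the best 1 of 20, 0.81 for the best 3 of 20, 0.78 for the best 1 of 100, 0.89 for the best 3 of 100 and 0.94 for the best 5 of 100. A short list therefore helps only if it is fixed before the data are seen.

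**Step 5: which validation.** Leave-one-out accuracy is right on average but noisy: at P = 3 it ran from 0.23 to 0.70 across null data sets. An AUC from leave-one-out scores pooled across subjects is also biased downward, averaging about 0.43 at P = 1 and 0.47 at P = 3 when the truth is 0.50.

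**The case against.** The strongest reply is that the plan never says the fitting subjects will be scored. Taken literally, an ROC built on new-subject scores is compatible with cross-validation, and the wording is permissive about both the technique and the ROC. That is fair: this is an unspecified step, not a stated error. But defining a symbol does not supply subjects, and with no validation described, the analysis as written can be carried out only on the fitting sample.

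Three stronger readings are tempting, and the documents do not support them.
- A reader might infer that a high AUC is bound to appear with no signal. That depends on P, which is not given. The stated imaging hypotheses are narrow (amygdala and vmPFC, with insula and hypothalamus as further nodes), and 1 to 3 fixed parameters give a null AUC of only 0.58 to 0.67. The wider candidate list in the fMRI analyses text makes large inflation plausible, not certain.
- A reader might take the n + m − 2 note as a plan to use up to 27 parameters. It is a mathematical condition for the inverse, not a chosen P.
- A reader might infer that the study's main conclusions rest on this ROC. None of the specific aims in Section B includes classification, and the statement about biomarkers under Outcome measure and Impact concerns the study as a whole. The primary outcome, the Nausea Severity Scale, is unaffected.

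It also stands that 15 v 15 is not written in the classifier text, and that pooling the two patient groups reduces the inflation without removing it.

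**Conclusion.** The concern holds in conditional form. The plan promises sensitivity, specificity and ROC curves but provides neither new subjects nor internal validation, so as written these figures would come from the fitting data. With no true signal, the mean apparent AUC reaches about 0.80 at P = 8 for 15 v 15, and passes 0.80 between P = 10 and P = 15 for 15 v 30. Selection on the same data reaches that level with far fewer parameters. Only a very small list fixed in advance keeps the inflation modest, and even then it is not zero.

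These sizes rest on normally distributed parameters, complete scans in every group, and an assumed P and m. The point is confined to an exploratory analysis in the optional imaging sub-study.

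**What to change.** Amend the fMRI analyses text as follows.
- Name a short list of imaging parameters before any group comparison, for example those tied to the amygdala–vmPFC hypothesis, and state which groups form n and m.
- Keep n + m − 2 > P as a mathematical requirement only, and apply it to the training part of each fold. With 5 folds of 15 v 15, for example, 12 + 12 − 2 = 22 must exceed P.
- Estimate sensitivity, specificity and AUC by repeated stratified k-fold cross-validation. Compute the AUC within folds, or by leave-pair-out (15 × 15 = 225 pairs, or 15 × 30 = 450), rather than from pooled leave-one-out scores. Repeat any parameter selection inside each fold.
- Give a permutation p-value for the whole procedure, including selection.
- Label any ROC computed on the fitting subjects as apparent and exploratory, not as diagnostic performance.

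The cost is SAP wording and a little more code, with no added subjects, scans or visits. The reported AUC will be less favourable and visibly imprecise at this sample size.
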